## 24.3. Appendix 3 - Patient Activation Measurement

Below are some statements that people sometimes make when they talk about their health. Please indicate how much you agree or disagree with each statement as it applies to you personally by circling your answer. There are no right or wrong answers, just what is true for you. If the statement does not apply to you, circle N/A.

| 4 | I am the person who is responsible for taking care of my health.   | Disagree
Strongly | Disagree | Agree | Agree
Strongly | ₹
Ž |
|----------|--|----------------------|----------|-------|-------------------|--------|
| 5        | Taking an active role in my own health care is the most important thing that affects my health.                          | Disagree
Strongly | Disagree | Agree | Agree
Strongly | ¥
N |
| ر
ب   | I am confident I can help prevent or reduce problems associated with my health.  | Disagree
Strongly | Disagree | Agree | Agree
Strongly | K/A    |
| 4        | I know what each of my prescribed medications do.  | Disagree
Strongly | Disagree | Agree | Agree
Strongly | N/A    |
| ικi      | I am confident that I can tell whether I need to go to the doctor or whether I can take care of a health problem myself. | Disagree
Strongly | Disagree | Agree | Agree
Strongly | N/A    |
| نو       | I am confident that I can tell a doctor or
nurse concerns I have even when he or
she does not ask.                 | Disagree
Strongly | Disagree | Agree | Agree
Strongly | N/A    |
| 7.       | I am confident that I can carry out medical treatments I may need to do at home.   | Disagree
Strongly | Disagree | Agree | Agree
Strongly | A/A    |
| ထံ       | I understand my health problems and what causes them.  | Disagree
Strongly | Disagree | Agree | Agree
Strongly | Z/A    |
| ග | I know what treatments are available for my health problems.   | Disagree
Strongly | Disagree | Agree | Agree
Strongly | N/A    |
| 10.      | 
 
I have been able to maintain lifestyle
changes, like healthy eating or exercising.
 
               | Disagree
Strongly | Disagree | Agree | Agree
Strongly | X
X |
| ξ.       | . I know how to prevent problems with my health.   | Disagree
Strongly | Disagree | Agree | Agree
Strongly | N/A    |
| 12.      | . I am confident I can work out solutions
when new problems arise with my health.                                     | Disagree
Strongly | Disagree | Agree | Agree
Strongly | Š
Ž |
| 13.      | . I am confident that I can maintain lifestyle changes, like healthy eating and exercising, even during times of stress. | Disagree
Strongly | Disagree | Agree | Agree
Strongly | N/N    |

## 24.4. Appendix 4 - Health Related Quality of Life

EQ-5D-5L

Under each heading, please tick the ONE box that best describes your health TODAY

MOBILITY

I have no problems in walking about  ${\mathbb N}$ 

I have slight problems in walking about  $\ensuremath{\mathbb{R}}$ 

I have moderate problems in walking about 🛭

I have severe problems in walking about  $\ensuremath{\mathbb{N}}$ 

I am unable to walk about oxtimes

SELF-CARE

I have no problems washing or dressing myself  $\ensuremath{\mathbb{N}}$ 

I have slight problems washing or dressing myself  $\ensuremath{\mathbb{N}}$ 

I have moderate problems washing or dressing myself  $\ensuremath{\mathbb{N}}$ 

I have severe problems washing or dressing myself  $\ensuremath{\mathbb{R}}$ 

I am unable to wash or dress myself  $\ensuremath{\mathbb{N}}$ 

USUAL ACTIVITIES (e.g. work, study, housework, family or leisure activities)

I have no problems doing my usual activities  $\ensuremath{\mathbb{R}}$ 

I have slight problems doing my usual activities  $\ensuremath{\mathbb{N}}$ 

I have moderate problems doing my usual activities  $\ensuremath{\mathbb{R}}$ 

I have severe problems doing my usual activities  $\ensuremath{\mathbb{N}}$ 

I am unable to do my usual activities  $\ensuremath{\mathbb{R}}$ 

PAIN / DISCOMFORT

I have no pain or discomfort  $\ensuremath{\mathbb{N}}$ 

I have slight pain or discomfort 🛭

I have moderate pain or discomfort 🛭

I have severe pain or discomfort  ${\mathbb N}$ 

I have extreme pain or discomfort ⊠

ANXIETY / DEPRESSION

I am not anxious or depressed  ${\mathbb N}$ 

I am slightly anxious or depressed 🛭

I am moderately anxious or depressed  $\ensuremath{\mathbb{R}}$ 

[figure not shown]
I am severely anxious or depressed  $\ensuremath{\mathbb{R}}$ 

I am extremely anxious or depressed  $\ensuremath{\mathbb{N}}$ 

which the best state you can imagine is marked 100 and we have drawn a scale (rather like a thermometer) on To help people say how good or bad a health state is, the worst state you can imagine is marked 0.

bad your own health is today, in your opinion. Please do We would like you to indicate on this scale how good or this by drawing a line from the box below to whichever point on the scale indicates how good or bad your health state is today.

Your own health state today

## 24.5. Appendix 5 - Mental wellbeing

WHO-5 Well-being Index

| m pr     | Please respond to each item by marking one box per row, regarding how you felt in the last two weeks. | All of
the time | Most
of the
time | More
than half
the time | Less
than half
the time | Some
of the
time | At no
time |
|----------|---|--------------------|------------------------|-------------------------------|-------------------------------|------------------------|---------------|
| WHO
1 | I have felt cheerful in good spirits.   | 5                  | □ 4                    | e                             | 2                             |  -              | o             |
| WHO
2 | I have felt calm and relaxed.   | 5                  | 4                      | _
B                        | 2                             |                        | o             |
| WHO 3    | I have felt active and vigorous.  |                    | 4                      | 3                             | 2                             | -               | o             |
| WHO *    | I woke up feeling fresh and rested.   | s                  | 4               | ღ                             | 2                             | -               | o             |
| WHO
8 | My daily life has been filled with things that interest me.   | 2                  | □4                     | _ ღ                           | 2                             | □ ~             | °             |

Dianea from nuar

## 24.6. Appendix 6 - Ostomy Skin Tool (OST) V2.0

# Ostomy Skin Tool V2.0 - PRO (Patient Reported Outcome) Questionnaire

### Patient questionnaire

| Date:/_                                 |  |
|---|--|
|   |  |
| 1 |  |
| Patient number                          |  |

Instructions

These questions should be completed by the patient themselves. The following questions ask about the skin complications you experience around your stoma (from the storna site to the edge of the storna bag adhesive). Please answer each question thinking about right now when changing your product.

Question 1. Do you experience any bleeding from the skin around your stoma right now when changing your product? (sick one box only)

| Not experiencing |
|------------------|
| Experiencing     |

Question 2. Once you have cleaned and dried the skin, do you still experience any weeping or moisture on the skin around your stoma right now when changing your product? (fick one box only)

| Not experienci   |  |
|--|--|
| The state of the s |  |
|  |  |
| Experiencing   |  |
|  |  |

Question 3. Are you experiencing any ulcers or sores around your stama right now when changing your product? (tick one box only)

|   | Not experiencing |
|---|------------------|
| 0 | Ехреі            |

## Instructions

Instructions

The following questions ask about the skin complications you experience around your stoma (from the stoma size to the edge of the stoma bog adhesive). Please answer each question thinking about the period since you last changed your product until now.

### Patient questionnaire

| C | ב |    |
|---|---|----|
|   |   |    |
|   |   |    |
|   |   |    |
|   |   |    |
|   |   |    |
|   |   |    |
|   |   |    |
|   |   |    |
|   |   |    |
|   |   |    |
|   |   |    |
|   |   |    |
|   |   |    |
|   |   |    |
|   |   |    |
|   |   |    |
|   |   |    |
|   |   |    |
|   |   |    |
|   |   |    |
|   |   |    |
|   |   |    |
|   |   |    |
|   |   |    |
|   |   |    |
|   |   |    |
|   |   |    |
|   |   | ī  |
|   |   | J  |
|   |   | 1  |
|   |   |    |
|   |   | 1  |
|   |   |    |
|   |   | 1  |
|   |   | i  |
|   |   | 1  |
|   |   | 1  |
|   |   | ij |
|   |   | ı  |
| 1 |   | 1  |
|   | ī |    |
|   | × |    |
| 4 | 2 |    |
|   | Е |    |
|   | = | i  |
|   |   | i  |
|   | _ |    |
| 4 | 벋 | 1  |
|   | Ę | ŀ  |
| J | ψ | )  |
| • |   | ì  |
|   | ۵ | 1  |
| ć | ĭ | ,  |
| • | _ |    |
|   |   |    |
|   |   |    |
|   |   |    |

Question 5. Please rate on a scale from 0-10 how painful the skin around your stoma has been at its  $\frac{1}{100}$ 

|   | 10
Worst
possible
periotomal |
|---|---------------------------------------|
|   | 6                                     |
|   |                                       |
|   | -                                     |
|   | و                                     |
|   | 5                                     |
|   |                                       |
|   |                                       |
|   | 2                                     |
| 0 | )
Very måd
pom                  |
|   | No pain                               |

Question 6. Please rate on a scale from 0-10 any burning feelings from the skin around your stoma

|   |   | 10
Worst
poxsible
periztomal
skin burning |
|---|---|---|
|   |   | 0   |
|   | o |   |
| •   |   | 2   |
| its worst since you last changed your product (tick one box only) |   | 9   |
|   |   | •   |
|   |   |   |
| d your p  |   | m   |
| change  |   | 2   |
| ince you last   |   | Yery mild
burning                                  |
| at its worst s  |   | No burning  |

## Question 7 (surrogate for picture of skin)

[figure not shown]
Please evaluate the amount of skin redness in the area around the stoma where your baseplate appliance is placed.

There is no skin redness:

There is skin redness between 0-10 cm² (up to around 3cm\*3cm)

There is more than 10 cm² of skin with redness (one or more areas with redness and total red area larger than 3.5cm\*3.5cm)

Ostomy Skin Tool V2.0 - Decision Tree score; subjects will be classified into No treatment required (0), mild (1), moderate (2) or severe (3) skin complications severity level based on the PRO data from OST V2.0 and the skin redness (Question 7)

## 24.7. Appendix 7 – System Usability Score

### System Usability Scale

Instructions: For each of the following statements, mark one box that best describes your reactions to the product today.

|    | St.
dir.  | Strongly
disagree |  | S | Strongly
agree |  |
|----|--|----------------------|--|---|-------------------|--|
| 1  | I think that I would like to use this system frequently.                                   |                      |  |   |                   |  |
| 2  | I found the system unnecessarily complex.  |                      |  |   |                   |  |
| m  | I thought the system was easy to use.  |                      |  |   |                   |  |
| 4  | I think that I would need the support of a technical person to be able to use this system. |                      |  |   |                   |  |
| 5  | I found the various functions in this system were well integrated.                         |                      |  |   |                   |  |
| 9  | I thought there was too much inconsistency in this system.                                 |                      |  |   |                   |  |
| 7  | I would imagine that most people would learn to use this system very quickly.              |                      |  |   |                   |  |
| œ  | I found the system very cumbersome to use.   |                      |  |   |                   |  |
| 6  | I felt very confident using the system.  |                      |  |   |                   |  |
| 10 | 10 I needed to learn a lot of things before I could get going with this system.            |                      |  |   |                   |  |
|    |  |                      |  |   |                   |  |

| O   | Registration/measurements   | PERFORMED BY             | Visit 1
(0 days) | Visit 2
4 weeks | 6 weeks | 6 weeks 8 weeks | 10 weeks | Visit 4
10 weeks Termina-
tion | Ongoing |
|-----|---|--------------------------|---------------------|--------------------|---------|-----------------|----------|--------------------------------------|---------|
|     |   | A. Primary endpoint      | ooint               |                    |         |                 |          |                                      |         |
| ⋖   | Leakages onto clothes Think back on the last 2 weeks; how many times have you experienced stoma effluent leakage outside the baseplate (e.g. onto clothes or bedsheets)? (number) | Subject                  | ×                   | ×                  | ×       | ×               | ×        | ×                                    |         |
|     | ш   | B. Secondary endpoint(s) | -                   |                    |         |                 |          |                                      |         |
| B.1 | PAM score (0-100) based on Patient Self-management (Patient Activation Measure (PAM)), Appendix 3   | Subject                  | ×                   | ×                  |         | ×               |          | ×                                    |         |
| B.2 | Emotional impact score (0-100) based on Leakage related QoL (OLI), Appendix 2   | Subject                  | ×                   | ×                  |         | ×               |          | ×                                    | 2       |
| B.3 | Usual/social activities score (0-100) based on Leakage related QoL (OLI), Appendix 2  | Subject                  | ×                   | ×                  |         | ×               |          | ×                                    |         |
| B.4 | Coping/Control score (0-100) based on Leakage related QoL (OLI), Appendix 2   | Subject                  | ×                   | ×                  |         | ×               |          | ×                                    |         |
| B.5 | EQ-5D-5L – index score (UK) based on Health R QoL (EQ5D-5L), Appendix 4   | Subject                  | ×                   | ×                  |         | ×               |          | ×                                    |         |
| B.6 | EQ-5D-5L – VAS score based on Health R QoL (EQ5D-5L), Appendix 4  | Subject                  | ×                   | ×                  |         | ×               |          | ×                                    |         |

|        | C. Exp  | Exploratory endpoint(s) |   |   |   |   |   |   |   |
|--------|---|-------------------------|---|---|---|---|---|---|---|
| 20     | N 40 5  | Subject                 | × | × |   | × |   | × |   |
| C.2    | WHO5 score (0-100) based on Mental wellbeing (WHO5), Appendix 5   | Subject                 | × | × |   | × |   | × |   |
| ن
3 | Worry about leakage  Think back on the last 2 weeks, to which degree did you worry about leakage? Very high degree - High degree - Some degree - Low degree - Very low degree In the last all | Subject                 | × |   | × |   | × |   |   |
|        |   |                         |   |   |   |   |   |   |   |
| C.3.1  | Worry about leakage  Only answered by subjects who have answered "Very high degree - High degree - Some degree" worry of leakage (C4).  | Subject                 | × |   | × |   | × |   |   |
|        | Why did you worry about leakage? (please tick all that apply (odour, embarrassment, soiling of clothes/bed sheets, skin issues, pain, other)  |                         |   |   |   |   |   | _ |   |
| C.4    | Feeling of security How is your feeling of security? Very poor, Poor, Acceptable, Good, Very good   |                         | × |   | × |   | × |   |   |
| පි     | Adverse Events (see termination form - ongoing)   | Nurse                   |   |   |   |   |   |   | × |
|        |   |                         |   |   |   |   |   |   |   |

| ۵   | D. Evalu   | Evaluation of Heylo device | e                      |                    |         |                    |             |                       |              |
|-----|--|----------------------------|------------------------|--------------------|---------|--------------------|-------------|-----------------------|--------------|
|     | Technical assurance/interoperability   |                            |                        |                    |         |                    |             |                       |              |
| 0.1 | Reliability of notifications  To which degree did you find the notifications from the App reliable and trustworthy? Not at all/Very low degree; Low degree; Some; High degree; Very high degree  |                            |                        |                    |         |                    |             | ×                     |              |
| D.2 | To which degree did you receive notifications timely to react on leakage? Not at all/Very low degree; Low degree; Some degree; High degree; Very high degree                                     |                            |                        |                    |         |                    |             | ×                     |              |
| D.3 | How stable did you find the overall system in everyday use?
Very unstable; Unstable; Somewhat stable; Stable; Very stable   | Subject                    |                        |                    |         |                    |             | ×                     |              |
| Ö   | Registration/measurements  | PERFORMED BY               | Visit 1
(0
days) | Visit 2
4 weeks | 6 weeks | Visit 3
8 weeks | 10
weeks | Visit 4 Termina- tion | Ongo-
ing |
|     | Usability/Interoperability   |                            |                        |                    |         |                    |             |                       |              |
| D.4 | System Usability Score (SUS), Appendix 7   | Subject                    |                        |                    |         |                    |             | ×                     |              |
|     | Evaluation of self-management  | ю                          |                        |                    |         |                    |             |                       |              |
| D.5 | To which degree did the Test Product make it easier to know when to change baseplate compared to only using usual stoma baseplate?  Much lower degree; lower degree; same degree; Higher degree. | Subject                    |                        |                    |         |                    |             | ×                     |              |
| D.6 | How was your confidence at night with Test Product compared to only using usual stoma baseplate? Much lower, lower, same, higher, much higher  | Subject                    |                        |                    |         |                    |             | ×                     |              |
| D.7 | To which degree did the Test Product give you peace of mind? Very low degree; Low degree; Some degree; High degree; Very high degree   | Subject                    |                        |                    |         |                    |             | ×                     |              |

|          | E. Evalua  | Evaluation of Heylo + Service                   | ice                    |                    |         |                    |             |                  |              |
|----------|--|---|------------------------|--------------------|---------|--------------------|-------------|------------------|--------------|
| E.1      | Preference Which product solution do you prefer? Stoma appliance alone without Test Product; Stoma appliance with Test Product (Heylo+Service)   | Subject   |                        |                    |         |                    |             | ×                |              |
| E.2      | Reason for preference What is your reason for preference? (Please tick all that apply) Body fit; Ability to bend and stretch; Feeling of security; Feeling of confidence; Less fear of leakage onto clothes; Discreet to wear, Discreetness in leakage control; Better sleep; Less embarrassment; Other + text | Subject   |                        |                    |         |                    |             | ×                |              |
| E.3      | Future use of product
If the Test Product was available today, would you start using it?
(Yes/No)  | Subject   |                        |                    |         |                    |             | ×                |              |
| E.4      | Recommendation of product to others  How likely would you be to recommend Heylo to other people with ostorny? Not at allivery unlikely: Unlikely; Neither/nor, Likely; Very likely   | Subject   |                        |                    |         |                    |             | ×                |              |
|          | F. Evaluation  | Evaluation of Coloplast Charter Support Service | Support                | Service            |         |                    |             |                  |              |
|   | Did you call Coloplast Charter Support Service during the study period? (Yes; No)  | Subject   |                        |                    |         |                    |             | ×                |              |
| No.      | Registration/measurements  | PERFORMED BY                                    | Visit 1
(0
days) | Visit 2
4 weeks | 6 weeks | Visit 3
8 weeks | 10
weeks | Visit 4 Termina- | Ongo-
ing |
| F.2      | Have you received any calls from Coloplast Charter Support Service during the study period? (Yes; No)  | Subject   |                        |                    |         |                    |             | ×                |              |
| F.3      | (if Y in F1 or F2) Did you find the call(s) helpful? Very much, Much; Some; Little; Very little/not at all   | Subject   |                        |                    |         |                    |             | ×                |              |
|          |  |   |                        |                    |         |                    |             |                  |              |

| F.4      | (if Y in F2) Did you retrieve calls from Coloplast Charter Support Service with an overall acceptable frequency? Yes; No, too many; No, too few  | Subject                      | ×   |
|----------|--|------------------------------|-----|
| F.5      | How likely would you be to recommend Coloplast Charter Support Service to other people with ostomy? Very likely; Likely; Neither/nor; Unlikely, Very unlikely/ not at all  | Subject                      | ×   |
| ×        | G. Evalu   | Evaluation of Heylo by nurse |     |
| 6.1      | How was it to onboard subject to Heylo? Very difficult; Difficult; Acceptable; Easy; Very easy   | Study nurse                  | ×   |
| 6.2      | How was it to train subject in using Heylo? Very difficult, Difficult, Acceptable;
Easy, Very easy  | Study nurse                  | ×   |
| .3
.3 | To which degree does Heylo support subject in how to manage their stoma? Very low degree; Some degree, High degree, Very high degree   | Study nurse                  | ×   |
| 6.4      | To which degree does Test Product (Heylo + Service) give subject better routines? Very low degree; Low degree; Some degree, High degree, Very high degree  | Study nurse                  | * × |
| 6.5      | Which product would you recommend to your patients? Standard of Care*Standard of Care + Test Product (Heylo + Service) Standard of Care + Test Product (Heylo + Service) but depends on the health situation of the patient. *Current stoma appliances in the market without Heylo | Study nurse                  | ×   |
|          |  |                              |     |

| Ä                           | Registration of AE/SAE/termination | lon |   |   |  |
|-----------------------------|------------------------------------|-----|---|---|--|
| Registration of termination | 11                                 |     |   |   |  |
| AEs/ADEs/SAEs/SADEs         | Investigator                       | ×   | × | × |  |
| Termination form            | Investigator                       |     |   | × |  |

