### **Exploratory endpoints**

- Skin condition measured by Decision Tree Score (0-3) based on Peristomal Skin Health (OST 2.0)
- Quality of Life WHO5 score (0-100) based on Mental wellbeing (WHO5)
- Worry about leakage (5-point scale)
- Feeling of security (5-point scale)
- Technical assurance/interoperability measured by system reliability, notification frequency and stability (all measures on 5-point scales)
- Usability and self-management evaluated through System Usability Score (0-100) and confidence measures (5-poins scales)
- Preference, recommendation and future use (5-point scales)
- Adverse events

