### Leakage service

If subjects have leakage issues, they have the possibility to call Coloplast Charter for Leakage support, and/or Coloplast Charter may reach out to the subject if subject is struggling with leakage (observed from Heylo app leakage data in cloud). In case subjects have questions related to how to change appliance or how to use/interpret the information provided by the HeyloTM app, subjects can also call Coloplast Charter Support through the HeyloTM app (number is provided in the app).

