### Evaluation of Heylo device (Questions, scale and assessment time Appendix 8, D)

- Technical assurance/ interoperability
  - Reliability and timing of notifications
  - System stability
- Usability/interoperability
  - Usability and ease of use evaluated through System Usability Score (0-100) (Appendix 7)
  - Other evaluations of self-management, and self-confidence
    - o Easiness in knowing when to change appliance
    - Confidence at night
    - o Peace of mind
    - o Adverse events

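### Notification frequency is a declared exploratory component with no item or named source, and the reliability and timeliness items (D.1, D.2) have no answer for a subject who received no notification

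*Combined protocol and SAP*

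**What the plan says.** The exploratory endpoints in the synopsis include "Technical assurance/interoperability measured by system reliability, notification frequency and stability (all measures on 5-point scales"). Section 5.3, under the evaluation of the device, lists "Reliability and timing of notifications" and system stability; frequency does not appear.

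Appendix 8 part D has three items under technical assurance, all at the termination visit only:

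- D.1, reliability: "To which degree did you find the notifications from the App reliable and trustworthy? Not at all/Very low degree", then four higher degrees.
- D.2, timeliness: "To which degree did you receive notifications timely to react on leakage? Not at all/Very low degree", then four higher degrees.
- D.3, stability: "How stable did you find the overall system in everyday use", with five answers.

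The one item in Appendix 8 that asks about frequency is F.4, which concerns support calls: "if Y in F2) Did you retrieve calls from Coloplast Charter Support Service with an overall acceptable frequency". Section 4.2 shows that app data reach the sponsor's service, because an adviser may contact a subject whose leakage problem is "observed from Heylo app leakage data in cloud". No section names those data as the source of an endpoint.

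**The concern.** Detecting leakage and notifying the user is the intended purpose of the device (section 4.5), and interoperability belongs to a stated secondary objective (section 3.1). D.1 to D.3 are the only items under technical assurance. Two gaps weaken them.

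First, followed as written, the plan produces no data for one declared component. Section 11.1.1 limits the case report forms to data that the plan refers to, so nothing fills the gap by default.

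Second, a subject who had no notification has nothing to rate in D.1 or D.2. If that subject chooses the lowest answer to D.2, a good outcome (nothing leaked) is counted together with two device failures (leakage not detected, leakage notified late). If the subject skips, the reader cannot tell this from ordinary non-response. Each item is asked once, so no later questionnaire resolves it.

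**Working it through.** The plan gives no figure for this endpoint. Its only design calculation (section 10.2) concerns the primary endpoint and is not affected, so most of the check is a comparison of the text.

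**1. Components against items**

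| Component | Synopsis | Section 5.3 | Appendix 8 |
|---|---|---|---|
| Reliability | yes | yes | D.1 |
| Notification frequency | yes | no | none |
| Timing of notifications | no | yes | D.2 |
| Stability | yes | yes | D.3 |

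**2. Possible substitutes for a frequency item**

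- F.4 asks about calls, not app notifications.
- In Appendix 9 an app notification is one tick-box reason for changing the baseplate, with up to three reasons ticked for the last 2 weeks. This is neither a count nor a 5-point scale.
- The call adviser's form lists a type of notification as a reason for a call, so it covers only subjects with a call.
- The app data in section 4.2 could give a count, but are not named as a source.

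**3. Routing.** C.3.1 goes only to subjects with at least some worry, F.3 only to those with a call, and F.4 only to those who received one. The PAM and the OLI social items offer a not-applicable answer. D.1 and D.2 have neither device.

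**4. What a subject without a notification would do.** The lowest D.2 label is the closest literal fit. Skipping is also possible: section 9.1.3 states forced completion for the eCRF, subjects answer in a separate part of the system (section 11.1.1), and section 10.1 bases its summaries on non-missing data.

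**5. Illustration of size.** Let N be the number of responders, q the share without a notification, and b the share of notified subjects who choose the lowest answer. From section 10.2, 60 × 0.75 = 45, used here as N. That figure counts subjects with leakage data at baseline and after at least 4 weeks, so the number answering D.2 at termination may differ. The documents do not give q or b. Assume b = 5% and a mean of 4 (scale 1 to 5) among notified subjects.

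If all subjects without a notification choose the lowest answer:

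- share in the lowest category = q + (1 − q) × b
- shift in the mean = q × 1 + (1 − q) × 4 − 4 = −3q

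| q | Subjects, 45 × q | Lowest-category share | Shift in mean | N if all skip, 45 × (1 − q) |
|---|---|---|---|---|
| 5% | 2.25 | 0.05 + 0.95 × 0.05 = 9.75% | −0.15 | 42.75 |
| 10% | 4.5 | 0.10 + 0.90 × 0.05 = 14.5% | −0.30 | 40.5 |
| 20% | 9 | 0.20 + 0.80 × 0.05 = 24.0% | −0.60 | 36 |

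If all of them skip, the lowest-category share stays at 5%, the mean does not move, and only N falls. The shares and shifts do not depend on N.

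**The case against.** The strongest case on the other side has four parts.

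- **A slip in the synopsis.** Section 5.3 and Appendix 8 agree with each other, so the synopsis may simply be misworded. That is possible, but the current text still declares a component that is not collected. A reader might infer that the timeliness item replaced a frequency item. The change log records no such step, and the documents show only a mismatch.
- **Few subjects may be affected.** The sensors detect leakage and moisture under the baseplate, use lasts 12 weeks, and subjects are selected for liquid or mushy output. Almost everyone may receive some notification. This stands: q is unknown and could be close to zero.
- **The lowest category need not be inflated.** A reader might infer that every subject without a notification lands in the worst category. The documents do not establish this, because such subjects can skip the item or choose another answer. It would also be wrong to take them for the subjects in whom the device worked best: silence can reflect missed leakage or a connection fault, which the technical support form lists. For the same reason, reporting only notified subjects would remove complete detection failures from the result. This stands and shapes the fix.
- **Frequency could still be reported.** The sponsor holds app data, and section 10.1 permits other summaries. So it does not follow that the report could say nothing about frequency. What is missing is a declared source and definition.

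**Conclusion.** The point holds in a limited form. The synopsis declares notification frequency, and no item or named source captures it. D.1 and D.2 lack a filter or an answer for subjects without a notification, so the lowest D.2 category may mix no leakage, missed leakage and late notification.

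The size cannot be fixed from the documents. It runs from no shift at all (nobody without a notification, or all such subjects skipping) to about 9 of 45 responders if 20% had none and all chose the lowest answer. Those shares are assumptions.

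The consequence is small: exploratory items asked once, no formal success criteria (section 10.4), and no effect on the primary endpoint or the sample size. This is a cheap improvement, not a flaw that threatens the study's conclusions.

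**What to change.** 1. Make the synopsis, section 5.3 and Appendix 8 agree. Add timeliness to the synopsis. Either drop notification frequency or name its source: a questionnaire item, or app data if the consent covers that use.
2. Add the answer *I received no notification* to D.1 and *I received no leakage notification* to D.2. The wording differs because D.1 asks about app notifications in general and D.2 about leakage. Follow both with a short question on whether leakage nevertheless occurred.
3. Report D.1 and D.2 for all responders, and again for notified subjects. Show subjects without a notification in rows of their own, split by whether leakage occurred, so that missed detections stay visible.

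The cost is one response option and a short follow-up in two items, some wording, and a slightly smaller denominator in the notified-only summary. Section 12 names changes to endpoints or assessment methods as significant, so the ethics committee would have to be notified. On the approximate dates in section 5.7, some subjects may have passed Visit 4 before any change takes effect; their answers should be identified as given on the old form.
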